C _{min}	Trough observed concentration
CNS	Central nervous system
CR	Complete response
CRF	Case report form
CT	Computed tomography
CTCAE	Common Toxicity Criteria for Adverse Events
CV	Coefficient of variation
CYP	Cytochrome P450
D/C	Discontinue
ECOG	Eastern Cooperative Oncology Group

Abbreviation or Term ¹	Definition/Explanation
eCRF	Electronic case report form
DLT	Dose Limiting Toxicity
ECG	Electrocardiogram
Eg	Exempli gratia (for example)
ET	Essential thrombocytosis / thrombocythemia
FACS	Fluorescence Activated Cell Sorting
FDA	Food and Drug Administration
FDG-PET	Fluorodeoxyglucose (FDG)-positron emission tomography (PET)
GCP	Good Clinical Practice
GFR	Glomerular filtration rate
GGT	Gamma glutamyl transferase
GLP	Good laboratory practice
HBsAg	Hepatitis B surface antigen
HBV	Hepatitis B virus
HCO ₃ ⁻	Bicarbonate
HCV	Hepatitis C virus
HIV	Human immunodeficiency virus
HR	Heart rate
hr	Hour or hours
IC ₅₀	Half maximal inhibitory concentration
i.e.	Id est (that is)
IEC	Independent ethics committee
IND	Investigational New Drug
INR	International normalized ratio
IRB	Institutional review board
IU	International unit
IV	Intravenous, intravenously
LDH	Lactate dehydrogenase
LLQ	Lower limit of quantitation
MedRA	Medical Dictionary for Drug Regulatory Activities
MRI	Magnetic resonance imaging
MRSD	Maximum recommended starting dose
MTD	Maximum tolerated dose
NOAEL	No-observed-adverse-effect level

Abbreviation or Term ¹	Definition/Explanation
NOEL	No-observed-effect-level
PDn	Pharmacodynamic(s)
PFS	Progression Free Survival
PK	Pharmacokinetic(s)
PO	Per os (administered by mouth)
PR	Partial response
PT	Prothrombin time
PTT	Partial thromboplastin time
QC	Quality control
RBC	Red blood cell
QD	Once daily
QTc	QT interval corrected
QTcF	QT interval corrected using Fredericia equation
QTcB	QT interval corrected using Bazett's formula
SAE	Serious adverse event
SD	Standard deviation or stable disease
T _{1/2}	Terminal elimination half-life
T ₃	Triiodothyronine
T ₄	Thyroxine
T _{max}	Time of maximum observed concentration
TID	Three times daily
TSH	Thyroid-stimulating hormone
ULN	Upper limit of normal
ULQ	Upper limit of quantitation
UV	Ultraviolet
WBC	White blood cell
WOCBP	Women of childbearing potential
WONCBP	Women of nonchildbearing potential

¹ All of these abbreviations may or may not be used in protocol.

PROTOCOL SIGNATURE

I confirm that I have read this protocol, and I will conduct the study as outlined herein and according to the ethical principles stated in the latest version of the Declaration of Helsinki, the applicable ICH guidelines for good clinical practice, and the applicable laws and regulations of the federal government. I will promptly submit the protocol to the IRB for review and approval. Once the protocol has been approved by the IRB, I understand that any modifications made during the study must first be approved by the IRB prior to implementation except when such modification is made to remove an immediate hazard to the subject.

I will provide copies of the protocol and all pertinent information to all individuals responsible to me who assist in the conduct of this study. I will discuss this material with them to ensure that they are fully informed regarding the study treatment, the conduct of the study, and the obligations of confidentiality.

This document is signed electronically through submission and approval by the Principal Investigator at Huntsman Cancer Institute in the University of Utah IRB Electronic Research Integrity and Compliance Administration (ERICA) system. For this reason, the Principal Investigator at Huntsman Cancer Institute will not have a hand-written signature on this signature page.

Instructions to multisite Principal Investigators at locations other than Huntsman Cancer Institute: SIGN and DATE this signature page and PRINT your name. Return the original, completed and signed, to the HCI Research Compliance Office. Retain a copy in the regulatory binder.

Signature of Principal Investigator

Date

Principal Investigator Name (Print)

Name of Institution

STUDY SUMMARY

Title	A Phase II Study to Evaluate the Efficacy and Safety of Selinexor in Patients with Myelofibrosis Refractory or Intolerant to JAK1/2 Inhibitors
Short Title	Selinexor in myelofibrosis refractory or intolerant to JAK 1/2 inhibitors
Protocol Identifiers (IRB – internal)	IRB # 114354 – CTO # HCI-17-HEM-13
IND number	140746
Phase	II
Design	Open label, non-randomized, prospective, single-arm study
Study Duration	Up to 30 months
Study Center(s)	Multisite
Objectives	To evaluate the efficacy, safety, and tolerability of selinexor in primary myelofibrosis (PMF), post-essential thrombocythosis myelofibrosis (PET-MF), or post-polycythemia vera myelofibrosis (PPV-MF) patients refractory or intolerant to ruxolitinib and/or any other experimental JAK1/2 inhibitors
Number of Subjects	Up to 24 subjects
Diagnosis and Main Eligibility Criteria	Inclusion: 
• Diagnosis of PMF or PET-MF or PPV-MF• Refractory or intolerant to ruxolitinib and/or any other experimental JAK1/2 inhibitors• Age \geq 18 years, ECOG \leq 2• Life expectancy \geq 6 months• Adequate hepatic, renal, and hematopoietic function Exclusion: 
• Prior exposure to a SINE compound, including selinexor• Radiation, chemotherapy, immunotherapy, or any other anticancer therapy within 2 weeks of C1D1• Major surgery within 4 weeks of C1D1• Uncontrolled active infection requiring treatment, active hepatitis A, B, or C infection• Active gastrointestinal dysfunction affecting absorption or ability to swallow
Study Product, Dose, Route, Regimen	Selinexor, 40-80 mg orally once weekly depending on cohort
Duration of administration	Until IWG-MRT progressive disease criteria for leukemic transformation have been met (appendix 5), subject experiences an intolerable toxicity, or is no clinical benefit per treating physician's discretion, whichever occurs first
Reference therapy	None

Statistical Methodology	
Primary Objective: Response is defined as a 35% or greater reduction in spleen volume as measured by MRI or CT abdomen from baseline to after 6 cycles of treatment. A sample size of 18 evaluable subjects will provide 83% power at one-sided alpha = 0.05 to reject a response rate of 15% (the null hypothesis) using a one sample exact test for a binomial proportion provided the true response rate is 42%. The null hypothesis will be rejected if 6 or more out of 18 subjects respond. The planned sample size is 24 to allow for up to a 25% dropout rate. Change and percentage change in radiographic spleen volume as well as radiographic spleen response rates will be summarized using descriptive statistics. The mean, range, standard deviation and 95% confidence interval will be reported for change and percent change in spleen volume.
 
Secondary Objectives: adverse events will be evaluated and graded as per the CTAEv5.0 and safety endpoints will be analyzed by descriptive statistics. Additional efficacy endpoints will be analyzed descriptively: response rates (overall response and symptoms response by IWG-MRT criteria) will be determined by tabulating the number and proportion of subjects that respond. The mean, standard deviation, minimum, and maximum time to response will be computed for the subset of patients that have a response.

-------------------------	---

1 OBJECTIVES

1.1 Primary Objective

To assess the efficacy of selinexor on spleen volume reduction in subjects with myelofibrosis (PMF, PET-MF, or PPV-MF) refractory or intolerant to ruxolitinib and/or any other experimental JAK1/2 inhibitors.

Primary Endpoint:

Response rate defined as the proportion of subjects with $\geq 35\%$ reduction in spleen volume as measured by MRI or CT abdomen from baseline to after six cycles of treatment. Patients who do not complete six cycles of therapy will be considered non-responders, but their data will still be reported. Patients who do not complete six cycles of treatment will receive an MRI at cycle 7 day 1, or at discontinuation of therapy (see section 11.4.2).

1.2 Secondary Objectives

- 1.2.1 To assess the safety/tolerability and further characterize the safety profile of selinexor in PMF, PET-MF, or PPV-MF patients refractory or intolerant to ruxolitinib and/or any other experimental JAK1/2 inhibitors.

Secondary Endpoints: rate of adverse events (AEs) and serious adverse events (SAEs).

- 1.2.2 To further assess the efficacy and clinical activity of selinexor (by means of reduction in symptoms, overall response, and overall survival) in subjects with myelofibrosis (PMF, PET-MF, or PPV-MF) refractory or intolerant to ruxolitinib and/or any other experimental JAK1/2 inhibitors.

Secondary Endpoints:

- Percent change of spleen volume as measured by MRI or CT abdomen.
- Proportion of patients with $\geq 50\%$ reduction of total symptoms score as measured by the MPN-Symptoms Assessment Form (MPN-SAF) from baseline to after 6 cycles of treatment. Patients who do not complete six cycles of therapy will be considered non responders, but their data will still be reported. Patients who do not complete six cycles of treatment will receive the MPN-SAF assessment at cycle 7 day 1, or at discontinuation of therapy (see section 11.4.2).
- Overall response rate according to the 2013 IWG-MRT consensus criteria for treatment response in primary and secondary MF (post-PV and post-ET).
- Overall survival at 24 months from the initiation of study therapy

1.3 Exploratory Objective(s)

- 1.3.1 To assess the effects of selinexor on MF bone marrow fibrosis grade.

Exploratory Endpoints: changes in bone marrow fibrosis grade and cytogenetic abnormalities from baseline.

1.3.2 To assess the effects of selinexor on duration of spleen volume reduction.

Exploratory Endpoints: Duration of $\geq 35\%$ reduction in spleen volume as measured by MRI or CT abdomen.

1.3.3 To assess the effects of selinexor on levels of circulating inflammatory cytokines.

Exploratory Endpoints: change in circulating inflammatory cytokine profile including but not limited to IL-6, IL-1 β , tumor necrosis factor (TNF), TNFRII.

1.3.4 To assess the effects of selinexor on JAK2 or CALR or MPL mutant allele burden.

Exploratory Endpoints: change in allele burden of JAK2V617F, MPLW515 and S505 and CALR exon 9.

1.3.5 To assess the effects of selinexor on genetic mutations by NGS.

Exploratory Endpoints: changes in genetic mutations by NGS from baseline.

1.3.6 To assess the effects of selinexor on other pharmacodynamic markers.

Exploratory Endpoints: change in other pharmacodynamic markers levels from C2D1 pre dose to 4 hours post dose.

1.3.7 To explore whether a customized tool can be developed to estimate spleen volume based on MRI or CT abdomen.

Exploratory Endpoints: correlation between spleen volumes calculated using the standard institutional method and a new experimental method.

1.3.8 To find predictive marker of selinexor response, from DNA and RNA sequencing.

Exploratory Endpoints: to identify predictive markers of selinexor response from DNA and RNA sequencing.

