4.2 Number of Patients

The study will enroll up to 24 patients. The power calculation for efficacy is based on a sample size of 18 response-evaluable patients. The sample size was set to 24 to allow for enrollment of up to 6 patients who are not evaluable.

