5.1 Inclusion Criteria

Yes/No (Response of "no" = patient ineligible)

- 5.1.1 Male or female subject aged \geq 18 years.
- 5.1.2 Eastern Cooperative Oncology Group (ECOG) performance status \leq 2
- 5.1.3 Diagnosis of primary myelofibrosis (PMF), post-essential thrombocythosis myelofibrosis (also known as thrombocythemia) (PET-MF) or post-polycythemia vera myelofibrosis (PPV-MF).
- 5.1.4 Life expectancy \geq 6 months.
- 5.1.5 Prior treatment with ruxolitinib or any experimental JAK1/2 inhibitor with any one or more of the following:
- Inadequate response after being on \geq 3 months of treatment defined by:
 - Palpable spleen \geq 10 cm below the left subcostal margin on physical examination at the screening visit OR
 - Palpable spleen \geq 5cm below the left subcostal margin on physical examination at the screening visit AND active symptoms of MF at the screening visit defined presence of 1 symptom score of \geq 5 or two symptom scores each of \geq 3 using the Screening Symptoms Form (Appendix 6)
 - Intolerant to ruxolitinib and/or other JAK1/2 inhibitors due to any grade \geq 3 non-hematologic AEs or any grade \geq 2 AEs requiring treatment discontinuation AND palpable spleen \geq 5cm below the left subcostal margin on physical examination at the screening visit.
- 5.1.6 Adequate organ function as defined as:
- **Hematologic** (\leq 28 days prior to C1D1):
 - Total white blood cell (WBC) count \geq 1000/mm³
 - Absolute neutrophil count (ANC) \geq 500/mm³
 - Hemoglobin \geq 7 g/dL
 - Platelet count \geq 30,000/mm³

For patients receiving transfusion and growth factor support, the following delays must be observed between the last administration and hematologic laboratory screening assessments:

- For hematopoietic growth factor support (including erythropoietin, darbepoetin, granulocyte-colony stimulating factor [G-CSF], granulocyte macrophage-colony stimulating factor [GM-CSF], and platelet stimulators [e.g., eltrombopag, romiplostim, or interleukin-11]): at least 2 weeks.

Growth factor support, RBC and/or platelet transfusions are allowed as clinically indicated per institutional guidelines during the study.

- **Hepatic** (\leq 28 days prior to C1D1):
 - Total bilirubin $< 1.5 \times$ ULN except in patients with indirect hyperbilirubinemia due to hemolysis or gilbert's syndrome where total bilirubin should be $< 5X$ ULN
 - Aspartate aminotransferase (AST) and alanine aminotransferase (ALT) $< 2.5 \times$ ULN.

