- 11 CBC with differential includes hemoglobin, hematocrit, mean corpuscular volume, mean corpuscular hemoglobin, mean corpuscular hemoglobin concentration, white blood cell (WBC) count, WBC differential, RBC count, lymphocytes, monocytes, neutrophils, band neutrophils, eosinophils, basophils, platelets. WBC differential may be automated or manual as per institutional standards. Reticulocytes may be done only when clinically indicated. The baseline CBC need not be repeated if the screening CBC is performed within 7 days of C1D1.
- 12 Complete serum chemistry includes limited serum chemistry (as defined below) as well as, phosphate, magnesium, LDH, amylase, lipase, and uric acid. It is due at Screening or C1D1, then D1 of each subsequent Cycle, and EOT visit.

- 13 Limited chemistry includes sodium, potassium, chloride, calcium, bicarbonate, BUN, creatinine, glucose, total protein, albumin, ALT, AST, alkaline phosphatase, and total bilirubin. It is due at C1D8 and C1D15.
- 14 Includes prothrombin time (PT), international normalization ratio (INR), and activated partial thromboplastin time (aPTT).
- 15 Spleen volume will be measured by MRI (or CT abdomen if MRI is contraindicated) at screening, at C4D1 after completion of 3 cycles and at C7D1 after completion of 6 cycles, allowing up to 4 weeks after cycle 7 D1. Additional MRIs will be performed for patients continuing on study treatment at cycle 10 D1, cycle 13 D1, cycle 19 D1, C25D1 to assess spleen volume. Imaging modality should remain consistent throughout study for each patient. Screening MRI should be completed \leq 14 days prior to C1D1. An additional MRI will be performed at the End of Treatment for all patients including those who do not complete at least 6 cycles of study treatment unless death occurs. CT abdomen is acceptable if MRI is contraindicated for estimation of spleen volume.
- 16 Both posteroanterior and lateral films should be obtained at baseline. Note that this test does not need to be repeated if results are available from a test performed within 30 days prior to start of therapy. This test serves as a baseline in the event that patients develop any adverse events during the study.
- 17 For women of childbearing potential; negative serum β -hCG pregnancy test within 3 days of C1D1.

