11.2 Sample size determination

Response is defined as a 35% or greater reduction in spleen volume from baseline to after 6 cycles of treatment. A sample size of 18 evaluable subjects will provide 83% power at one-sided alpha = 0.05 to reject a response rate of 15% (the null hypothesis) using a one sample exact test for a binomial proportion provided the true response rate is 42%. The null hypothesis will be rejected if 6 or more out of 18 subjects respond. Patient who discontinued treatment and failed to receive 6 cycles of treatment would be considered as non-responders. The planned sample size is up to 24 to allow for up to a 25% dropout rate.

The alternative hypothesis is based on the known radiographic spleen response rate of ruxolitinib in MF patients and would indicate comparable efficacy.^{17,18} The radiographic spleen response rate of the standard therapy for patients who fail or can't tolerate ruxolitinib is unknown, and 15% was chosen as a response rate below the minimum clinically meaningful response rate.

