11.5.3 Exploratory endpoints

A statistical plan will be determined for exploratory endpoints prior to the initiation of the statistical evaluation.

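### Exploratory objective 1.3.7 asks whether a tool can estimate spleen volume, but its only endpoint is correlation; add mean difference and limits of agreement

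*Combined protocol and SAP*

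**What the plan says.** Section 1.3.7 states the objective as "To explore whether a customized tool can be developed to estimate spleen volume based on MRI or CT abdomen". The single endpoint listed under it is the "correlation between spleen volumes calculated using the standard institutional method and a new experimental method". The type of coefficient is not given.

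Section 11.5.3 is the only analysis text for exploratory endpoints: "A statistical plan will be determined for exploratory endpoints prior to the initiation of the statistical evaluation". Neither there nor elsewhere do the documents mention a mean difference, limits of agreement, a concordance measure or an acceptable error for comparing the two methods.

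Four other provisions bear on the comparison:

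- **Range of spleen sizes.** Section 5.1.5 requires a spleen palpable at least 5 cm or 10 cm, depending on the route of entry, "below the left subcostal margin on physical examination at the screening visit". It sets no maximum, and no volumes are given anywhere.
- **Repeated scans.** Footnote 15 of the Study Calendar (section 8) schedules imaging at screening, "at C4D1 after completion of 3 cycles and at C7D1 after completion of 6 cycles", with later scans for patients who continue. It does not say which scans the experimental method is run on.
- **Two modalities.** The same footnote says "CT abdomen is acceptable if MRI is contraindicated for estimation of spleen volume".
- **Number of patients.** Section 4.2: "The study will enroll up to 24 patients". Section 11.2 counts on 18 evaluable.

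**The concern.** Estimating a volume is a measurement question: how far is the tool's reading from the standard reading, and is the error systematic? Correlation answers a different one, namely how closely the two sets of readings follow a straight line. Three gaps follow.

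1. A tool that is always 300 mL high, or always 30% high, correlates perfectly with the standard. The coefficient cannot show whether calibration is needed.
2. For a given measurement error, the coefficient is larger when patients' spleens differ more. The design does not fix that spread, so the same tool could look good or mediocre depending on who enrols.
3. Even if bias is calibrated out later, the coefficient alone does not give the remaining error in mL or percent.

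If the coefficient is all that is reported, a reader cannot judge whether the tool is usable. A fixed offset would also distort percent change, the scale on which spleen response is defined in this trial, although no section uses the tool for that classification.

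**Working it through.** **Inputs.** From the documents: up to 24 patients, 18 evaluable, and the 35% reduction threshold. Spleen volumes and method errors are not given, so baseline *b*, offset *c*, between-patient CV and error SD below are assumptions shown over a range.

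**The plan's own figure.** None is stated for 1.3.7. The patient numbers come from the primary-endpoint calculation in section 11.2, which reproduces: rejecting at 6 or more of 18 gives exact power 83.7% at a true rate of 42% and exact type I error 4.19% at 15%; 18/(1 − 0.25) = 24. Nothing below changes these.

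**1. Fixed offset.** If the tool reads *V* + *c*, then *r* = 1.00. Its reading of percent reduction is

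tool reduction = true reduction × *b*/(*b* + *c*),

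so it reads 35% when the true reduction is 0.35 × (*b* + *c*)/*b*:

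| Offset *c* | *b* = 1500 mL | *b* = 2000 mL | *b* = 3000 mL |
|---|---|---|---|
| +300 mL | 42.0% | 40.3% | 38.5% |
| +100 mL | 37.3% | 36.8% | 36.2% |
| −100 mL | 32.7% | 33.3% | 33.8% |
| −300 mL | 28.0% | 29.8% | 31.5% |

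Example: a true fall from 2000 to 1300 mL is 35.0%. With +300 mL the tool gives 1 − 1600/2300 = 30.4%; with −300 mL, 1 − 1000/1700 = 41.2%.

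**2. Scale error.** With a factor of 1.3, 1 − (1.3 × 1300)/(1.3 × 2000) = 35.0%. A pure scale error cancels in percent change but still misstates volume, again with *r* = 1.00.

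**3. Dependence on spread.** Let the tool's error SD be 200 mL, so the limits of agreement are ±1.96 × 200 = ±392 mL in every case. With between-patient SD *s*, *r* = *s*/√(*s*² + 200²):

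| *s* | 300 mL | 600 mL | 1000 mL | 1500 mL |
|---|---|---|---|---|
| *r* | 0.83 | 0.95 | 0.98 | 0.99 |

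The tool is identical in each column; only the patients differ.

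**4. Error left after perfect linear calibration.** Residual SD as a fraction of mean volume is CV × √(1 − *r*²). For *r* = 0.95, √(1 − 0.9025) = 0.312; for *r* = 0.98, √(1 − 0.9604) = 0.199. Multiplying by 1.96:

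| | CV 15% | CV 30% | CV 60% |
|---|---|---|---|
| *r* = 0.95 | 9.2% | 18.4% | 36.7% |
| *r* = 0.98 | 5.9% | 11.7% | 23.4% |

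**5. Precision of agreement measures.** With one scan per patient, in units of the SD of the between-method differences, the 95% half-widths are *t*/√*n* for the mean difference and *t* × √(1/*n* + 1.96²/(2(*n* − 1))) for each limit:

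| | Mean difference | Each limit |
|---|---|---|
| *n* = 24 | 0.42 SD | 0.73 SD |
| *n* = 18 | 0.50 SD | 0.87 SD |

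For agreement on 35% status, 0 discordant of 24 has a two-sided 95% Clopper-Pearson upper limit of 1 − 0.025^(1/24) = 14.2%.

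**The case against.** The best counter-argument has four parts.

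*The coefficient is not specified.* A concordance or absolute-agreement intraclass coefficient would react to bias. With mean 2000 mL and CV 30% (SD 600 mL), a +300 mL offset gives a concordance coefficient of 2 × 600²/(2 × 600² + 300²) = 0.89, not 1.00. This is correct, but it is not the ordinary meaning of correlation, and such a coefficient would still depend on the spread of spleen sizes and give no error in mL.

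*The plan is still open.* Section 11.5.3 promises a plan before evaluation, and nothing forbids adding agreement measures. That makes the fix easy, but the endpoint is already worded as correlation only, and a plan following it literally could report nothing else.

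*The objective is modest.* It explores whether a tool can be developed and makes no claim that the methods are interchangeable. Correlation is informative at that stage because it reflects scatter, and bias can be calibrated later. This stands as a reason to keep correlation, but a developer still needs to know whether there is bias and how much error remains.

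*The illustrations and the remedy can be overdone.* The volumes and offsets are assumed, no section applies the 35% cut to the tool, and with at most 24 patients the limits will be imprecise. Deming regression needs an error-variance ratio, and the documents describe no replicate readings from which to estimate it. These points stand. They make the extras optional and argue for reporting confidence intervals, but they do not justify leaving out the mean difference and limits.

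**Conclusion.** The concern holds, as an improvement to consider. The named endpoint does not fully answer the objective: a high coefficient alone cannot show that the tool estimates volume accurately. How much this matters in practice cannot be derived from the documents. Over the assumed range of ±100 to ±300 mL offsets and 1500 to 3000 mL baselines, a tool with *r* = 1.00 would read 35% at true reductions from 28.0% to 42.0%. At *r* = 0.95 the error after calibration could be anywhere from 9.2% to 36.7% of mean volume. These figures assume a Pearson-type coefficient.

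The effect is confined to one exploratory objective. The primary and secondary endpoints, sample size, alpha and power are untouched.

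**What to change.** In 1.3.7, and in the plan promised in 11.5.3:

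- Add the mean difference (or mean percentage difference) between methods with 95% limits of agreement, on the log scale if error grows with volume, and with confidence intervals.
- Add a check for a fixed offset. Differences plotted against mean volume are enough; use a Deming intercept only if an error-variance ratio can be justified.
- Keep correlation as supporting description and name the coefficient.
- State which scans enter. If patients contribute several, allow for this with a patient random effect, or prespecify one time point.
- Describe MRI and CT patients separately if any have CT.
- Where the tool is run on both baseline and follow-up scans, also report agreement on percent change. A 2×2 table of 35% status is optional and will be imprecise.

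The cost is one line in 1.3.7, a short paragraph in the pending plan and a little more analysis, with no new scans. Agreement on percent change may need extra experimental readings if baseline and follow-up scans are not both already due to be processed with the tool.
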